6.4. Safety Analyses

Refer to SAPv3.0

6.4.1. Adverse Events

Adverse events analyses described in the SAPv3.0 will be repeated for adverse events captured during open-label phase. Overall summaries of TEAEs occurring during the double-blind phase and open-label phase will be provided. The overall summaries will include the number and percentage of subjects reporting at least one: TEAE; TESAE; TEAE by severity; treatment related TEAE; TEAE leading to study drug discontinuation; TEAE leading to study termination; inject site reaction and deaths.

Descriptive statistics summaries of subject incidence of AEs will be summarized for all TEAEs, treatment-related TEAEs, TESAEs, treatment-related TESAEs, TEAEs resulting in study drug discontinuation, TEAE with an outcome of death, TEAE at injection site, TEAE relevant to COPD exacerbation, TEAE (incidence rate \geq 5%) by SOC in alphabetical order and PT in descending order of frequency. Subject incidence of TEAEs will also be

summarized by PT in descending order of frequency. TEAE will be summarized by fibrosis status at Screening. Number of TEAEs will be summarized by SOC in alphabetical order and PT in descending order of frequency.

Descriptive statistics summaries of subject incidence of TEAE, TEAE at injection site, by SOC, PT, severity will be provided. Subjects will be counted once under the worst severity reported within each SOC and PT.

Descriptive statistics summaries of subject incidence of TEAEs by SOC, PT and relationship to investigation product will be provided. Subjects will be counted once under the closest relationship reported within each SOC and PT.

Descriptive statistics of exposure-adjusted incidence rate of TEAES by PT will be provided. The definition of exposure-adjusted incidence rate is the number of subjects experiencing the TEAE divided by the total exposure-time among subjects, where each subject's exposure in person-year is calculated as (date of last dose of study drug – date of first dose of study drug +1) / 365.25.

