FSH (post-menopausal females)	X										patier						
Clinical Labs (heme, coag, trop, chem, lipids, urinalysis) ⁴	Х		Pre-dose X	Х	х	Pre-dose X	х	х	Pre-dose X	Х	until last patient with fibrosis	Pre-dose X		х		х	х
PRO-C3/PRO-C6	X								X		brosi	Pre-dose X		X		x	x
Calculate APRI			Pre-dose X						Pre-dose X		receives	Pre-dose X (Weeks 40, 64, 88, 112, 136, and 160)		х		х	х
Anti-drug Antibodies	X		Pre-dose X			Pre-dose X			Pre-dose X		10 th dose	Pre-dose X				X	х
Z-AAT Level	X		Pre-dose X		X	Pre-dose X		X	Pre-dose X		se (W	Pre-dose X		х		Х	х
Serum Alpha-1 Antitrypsin Level	X		Pre-dose X		X	Pre-dose X		X	Pre-dose X		(Week 100)	Pre-dose X		х		Х	Х
Concomitant Meds/Therapies	X		X	х	X	X	Х	X	X	X	ē	х		х		Х	x
Adverse Events	X		X	X	X	X	X	X	X	X		X		X		X	X
Study Treatment			X			X			X			X					
Pharmacokinetics (PK)			Pre-dose, 1 hr, & 2 hr post-dose X	X					Pre-dose, 1 hr, & 2 hr post-dose X	X							
Phone Call to Assess AEs													X				
Phone Call to Assess for Pregnancy Post-dose															Х		

- 1. Pulmonary function testing includes: Spirometry including VC, FVC, FEV₁, FEV₁/VC, FEV₁/FVC, and DLCO. Pertinent study FEV₁ will be based on post-bronchodilation value. Spirometry testing at Screening is to determine inclusion/exclusion. Spirometry and DLCO may be repeated once per timepoint. Spirometry and DLCO should also be conducted any time a patient experiences a COPD exacerbation. For dosing visits between Week 28 and Week 196, DLCO can occur once every 6 months.
- 2. MRI hepatoscan will include magnetic resonance elastography (MRE), hepatic fat content by MRI-PDFF (or equivalent) and hepatic iron content. MRI should always be completed before biopsy (if performed on the same day) and after a 4-hour fast from food.
- 3. A complete physical exam (PE) is to be performed at Screening and Study Completion/Early Termination. A symptom-directed PE is to be performed at all other designated visits. Genitourinary exam may be deferred.
- 4. Patients should be fasting (water only) for a minimum of 2 hours prior to collection of the clinical labs.
- 5. A post-dose biopsy visit will occur at Week 48 (± 2 weeks) for patients with evidence of fibrosis at Screening. For patients beyond Week 48 at the time of IRB/EC approval of Protocol v4.0, the post-dose liver biopsy will be performed at Week 72 (± 4 weeks) or Week 96 (± 4 weeks).
- 6. The Study Completion visit can occur 4 to 12 weeks from the last study dose.

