6.4. Duration of the Study

The duration of the study is as follows:

Patients without fibrosis: up to 72 weeks, as follows:

Screening: up to 8 weeks

Dosing and Follow-up: up to 64 weeks. Study treatment will be administered on Day 1 and Week 4.

Patients with evidence of fibrosis: up to 216 weeks, as follows:

Screening: up to 8 weeks

Dosing through end of open-label phase: up to 196 weeks, followed by a Study Completion visit 4 to 12 weeks after the last dose in the open-label phase. Up to 18 doses of study treatment will be administered (Day 1, Week 4, Week 16 followed by a dose once every 12 weeks up to Week 196).

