4. DEFINITIONS AND DATA HANDLING

The following general data handling conventions, will be used in the derivation of variables used in summaries of the open-label phase data:

Term	Definition/Rule	
Baseline	The latest measurement performed prior to the first dose of open-label phase Fazirsiran.	
Study Day	(Date of assessment) – (date of first dose of open-label phase Fazirsiran) + 1, if date of	
	assessment \geq date of first dose of open-label phase Fazirsiran;	
	(Date of assessment) – (date of first dose of open-label phase Fazirsiran), if date of	
	assessment < date of first dose of open-label phase Fazirsiran	
TEAE	Adverse event that first occurred or worsened in severity following dose administration of	
	the first dose of open-label phase Fazirsiran through EOS or Early Termination	
TESAE	Serious adverse event that first occurred or worsened in severity following dose	
	administration of the first dose of open-label phase Fazirsiran through EOS or Early	
	Termination	

Table 1: Definitions

For other general definitions and data handling, refer to SAPv3.0.

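### The open-label exposure-adjusted incidence rate counts each subject once but keeps that subject's person-time after the first event, so it is not a first-event rate and moves with length of follow-up

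*SAP*

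**What the plan says.** The definition is in SAP Addendum 6.4.1 (Adverse Events), for a table by preferred term: "The definition of exposure-adjusted incidence rate is the number of subjects experiencing the TEAE divided by the total exposure-time among subjects". The time per subject follows: "each subject's exposure in person-year is calculated as (date of last dose of study drug – date of first dose of study drug +1", divided by 365.25. The addendum does not end a subject's time at the onset of the term.

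The events follow a different clock. In Table 1 of SAP section 4, a TEAE is one that starts or worsens after "the first dose of open-label phase Fazirsiran through EOS or Early Termination". For patients with fibrosis, footnote 6 to Protocol Table 2 says: "The Study Completion visit can occur 4 to 12 weeks from the last study dose". The window for events therefore runs beyond the window for exposure.

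The same SAP section also plans event counts: "Number of TEAEs will be summarized by SOC in alphabetical order and PT in descending order of frequency". It defines no rate of events per person-year.

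**The concern.** The numerator and denominator do not belong to the same kind of rate. Because subjects are counted, each can contribute at most one case per term. After the first onset a subject can add nothing more to the numerator but still adds time to the denominator. The result is neither first events per person-time at risk nor events per person-time.

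Two things follow. On a common window the value is below the first-event rate, and the gap grows with incidence. The value also falls as follow-up lengthens even when the hazard is constant, although exposure adjustment is meant to remove differences in follow-up. Open-label follow-up will vary. Dosing starts after a biopsy at Week 48, 72 or 96. It ends when the last fibrosis patient has the Week 100 dose or an extension study opens at the site, and at the latest at Week 196. Protocol 6.2 gives long-term safety as the purpose of this phase, and this is the addendum's only exposure-adjusted adverse event measure.

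**Working it through.** The documents print no exposure-adjusted rate, so there is no figure to reproduce. The check compares the written formula with a first-event rate.

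**Inputs.**
- Cumulative incidence p of a term: not in the documents; assumed, 5% to 70%.
- Hazard h: assumed constant.
- Start of open-label dosing: footnote 5 to Protocol Table 2 says "A post-dose biopsy visit will occur at Week 48 (± 2 weeks) for patients with evidence of fibrosis at Screening", with Week 72 or 96 for some patients. The next scheduled doses are Weeks 52, 76 and 100.
- Latest end of dosing, Protocol 6.4: "followed by a dose once every 12 weeks up to Week 196".
- Tail from last dose to Study Completion: 4 to 12 weeks.

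**Formula.** Let D be first-to-last-dose time and W the TEAE window, both in days. Then p = 1 − exp(−hW), the written rate is p/D, and

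written rate / first-event rate = [p / (−ln(1 − p))] × (W/D).

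**Step 1: counting effect alone (W = D).**

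| p | Ratio | Shortfall |
|---|---|---|
| 5% | 0.975 | 2.5% |
| 10% | 0.949 | 5% |
| 20% | 0.896 | 10% |
| 30% | 0.841 | 16% |
| 50% | 0.721 | 28% |
| 70% | 0.581 | 42% |

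The constant hazard matters. If 6 of 20 subjects followed for 337 days all have onset on day 1, the written rate is 6/(20 × 337/365.25) = 0.325 per person-year. The first-event rate is 6/((14 × 337 + 6 × 1)/365.25) = 0.464. The shortfall is 30%, against 16% under a constant hazard.

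**Step 2: dependence on follow-up.** Assume h = 0.5 per year and W = D = T years. The written rate is (1 − exp(−hT))/T. For Week 52 to 100 (337 days, T = 0.92) it is 0.40. For Week 52 to 196 (1,009 days, T = 2.76) it is 0.27. The hazard is the same in both.

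**Step 3: the formula on the documents' own windows.** Exposure stops at the last dose while events count on, so W = D + 28 or D + 84 days. The entries under each incidence are written rate / first-event rate.

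| Open-label doses | Tail | W/D | p = 10% | p = 20% | p = 50% | Break-even p |
|---|---|---|---|---|---|---|
| Week 76–100 | 4 weeks | 197/169 | 1.106 | 1.045 | 0.841 | 27% |
| Week 76–100 | 12 weeks | 253/169 | 1.421 | 1.342 | 1.080 | 58% |
| Week 52–100 | 4 weeks | 365/337 | 1.028 | 0.971 | 0.781 | 15% |
| Week 52–100 | 12 weeks | 421/337 | 1.186 | 1.120 | 0.901 | 37% |
| Week 52–196 | 4 weeks | 1037/1009 | 0.975 | 0.921 | 0.741 | 5% |
| Week 52–196 | 12 weeks | 1093/1009 | 1.028 | 0.971 | 0.781 | 15% |

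Below the break-even incidence the written rate is too high; above it, too low. A subject with a single open-label dose would add 1 day of exposure against a window of 29 to 85 days, which pushes the rate up sharply.

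**Step 4: the other reading of the start date.** The exposure formula does not limit the first dose to the open-label phase. If it means double-blind Day 1 while only open-label events count, D for a patient dosed to Week 100 is 701 days. With first open-label dose at Week 52, the ratio at p = 20% is 0.896 × 365/701 = 0.47 with a 4-week tail and 0.54 with 12 weeks. To Week 196 the ratios are 0.68 and 0.71. Most of that shortfall comes from the start date, not from counting subjects once.

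**Example (assumed).** Take 20 subjects dosed from Week 52 to 100, 10 of them with the term. The written rate is 10/18.45 = 0.542 per person-year. The first-event rate is 0.751 on the same window, 0.694 with the 4-week tail and 0.601 with the 12-week tail. The written rate is lower by 28%, 22% and 10% respectively.

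**The case against.** The strongest objection is that the counting effect does not settle which way the printed number is wrong. A reader might infer that rates of common TEAEs will be understated in print and that a correction would raise them. The documents do not support either inference. With the clock started at the first open-label dose, Step 3 shows the direction reversing at an incidence between about 5% and 58%, depending on span and tail. This stands, and it limits the conclusion. It does not rescue the formula: two errors that offset by an amount varying with incidence, span and tail do not make a valid rate. Correcting only the dates would leave the whole Step 1 shortfall.

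Other points also stand in part:
- The open-label data are to be summarised descriptively, at one selected dose, with no concurrent comparator. The rate is planned by preferred term and not by length of exposure, so the Step 2 contrast illustrates a property of the formula and is not a planned output.
- Precision is low. Five cases among 25 subjects (20%, assumed) give an approximate 95% range of exp(±1.96/√5), or 0.42 to 2.40 times the estimate. A 10% shift is small beside that.
- The formula is stated openly and event counts are tabulated, so subjects over total exposure could serve as a crude measure if labelled as one. The addendum labels it an incidence rate.
- SAP version 3.0 is not among the documents, so consistency with the double-blind tables cannot be checked. The addendum nevertheless gives its own explicit definition.

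**Conclusion.** The point holds as a defect of definition. As written, the measure is not an exposure-adjusted incidence rate: on a common window it falls below the first-event rate by an amount that grows with incidence (Step 1), and it changes with follow-up when the hazard does not. These sizes rest on assumed incidences and a constant hazard; early onset would make the shortfall larger.

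No net direction can be claimed for the formula as it stands. If exposure starts at the first open-label dose, only very common terms over long dosing are clearly understated, and less common terms or short dosing spans can be overstated. If exposure starts at double-blind Day 1, the rate is too low at every incidence checked, mainly because of that start date.

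The consequence is limited to how open-label adverse events are presented. No test, dose choice or other decision rests on this table. It is a minor correction.

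**What to change.** In SAP Addendum 6.4.1, replace the exposure definition with one of two options.

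1. **First-event rate.** For each preferred term, count person-time from the first open-label dose to the first open-label onset of that term. For subjects without the term, count to the end of the TEAE window (EOS or Early Termination).
2. **Event rate.** Put the number of events of the term over full person-time across that same window, and label it an event rate.

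Either option should be written together with the exposure start and end dates, since one sentence governs all three. If SAP version 3.0 uses a different definition for the double-blind tables, a footnote should say so.

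The cost is one sentence and, for option 1, a per-term person-time derivation in the table program. Design and data collection do not change. Printed rates may move either way. Under option 1, for Week 52 to 100 with a 12-week tail, the rate would fall by about 16% at 10% incidence (1/1.186 = 0.843) and rise by about 11% at 50% (1/0.901 = 1.11).

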Study Schema

Number of Doses: The number of fazirsiran doses administered to each patient varies, but a minimum of 2 and a maximum of 18 total doses will be administered to each patient in the study. **Patients without fibrosis** will receive 2 doses (one at Day 1 and one at Week 4). **Patients with fibrosis** will receive up to 18 doses (Day 1, Week 4, Week 16 followed by a dose once every 12 weeks). All patients will discontinue dosing once the last enrolled patient with fibrosis receives their 10th dose (Week 100 visit) or until a long-term extension study is available at the subject's study site, whichever comes first.

Study Duration: For patients without fibrosis, the duration of the study is approximately 72 weeks, with an 8-week Screening period and a 64-week study follow-up period. For patients with fibrosis, the duration of the study is up to 216 weeks, with an 8-week Screening period, a 196-week study dosing period (if all 18 doses are received), followed by a Study Completion visit performed within 4 to 12 weeks from the dosing visit.

Study Assessments:

Patients will undergo the following evaluations at regular intervals during the study (refer to the SOA): medical history, physical examinations, vital sign measurements (blood pressure [BP], temperature, heart rate [HR], respiratory rate [RR]), weight (at baseline), AE monitoring, electrocardiograms (ECGs), urine pregnancy test/follicle-stimulating hormone (FSH) (females), concurrent medication, pulmonary function testing (spirometry including vital capacity [VC], forced vital capacity (FVC), FEV₁, FEV₁/VC, FEV₁/FVC, and diffusing capacity for carbon monoxide [DLCO]) and sample collection for hematology, coagulation, biochemistry, lipids, cardiac troponin, urinalysis, urine cotinine, ADAs, drug screens, serum alpha-1 antitrypsin levels, serum fibrosis biomarkers, liver biopsy, MRI (where feasible and available), and FibroScan® (where available).

Study visits will occur during the Screening window (Day -60 to -1), and as per the SOA. A telephone follow-up will occur 90 days after the last dose (\pm 5) to verify compliance with contraceptive measures and absence of any known pregnancy. Clinically significant changes including AE will be followed until resolution is achieved, or until medically stable or the event is otherwise explained, or until the patient is lost to follow-up.

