1. INTRODUCTION AND OBJECTIVES OF ANALYSIS

1.1. Introduction

This document presents the statistical analysis plan (SAP) addendum for Arrowhead Pharmaceuticals, Protocol AROAAT2001: A Placebo-Controlled, Multi-dose, Phase 2 Study to Determine the Safety, Tolerability and Pharmacodynamic Effect of Fazirsiran in Patients with Alpha-1 Antitrypsin Deficiency (AATD) [SEQUOIA].

This SAP Addendum is based on the AROAAT2001, V6.0, protocol dated 29 August 2022. Per the final SAPv3.0 signed prior to study unblinding, "Data collected in an open label stage will be descriptively summarized". The purpose of this SAP Addendum is to provide further detail on these open-label phase descriptive statistics. Analyses that were described in the final SAPv3.0 will not be described again in this document.

The formats for the tables, figures, and listings (TFLs) described in this SAP are provided in a companion document. A table of contents for the TFLs will be included in the companion document.

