3.1. Population Definitions

The following population samples for analyses will be evaluated and used for presentation and analysis of data captured during the open-label phase:

• Open-label Phase Set: All subjects who receive at least one dose of Fazirsiran in the open-label phase.

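### Open-label exposure-adjusted TEAE rate: subjects are counted through EOS or Early Termination, but person-time stops at the last dose

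*SAP*

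**What the plan says.** The addendum describes its own purpose in section 1.1: "The purpose of this SAP Addendum is to provide further detail on these open-label phase descriptive statistics". Its analysis set (section 3.1) is "All subjects who receive at least one dose of Fazirsiran in the open-label phase".

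Two of its definitions bear on this rate.

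- **Numerator window (section 4, Table 1).** A TEAE is an event that first occurs or worsens after "the first dose of open-label phase Fazirsiran through EOS or Early Termination".
- **Rate (section 6.4.1).** "The definition of exposure-adjusted incidence rate is the number of subjects experiencing the TEAE divided by the total exposure-time among subjects". A formula then fixes how much time one participant adds to that total: "exposure in person-year is calculated as (date of last dose of study drug – date of first dose of study drug +1) / 365.25".

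On follow-up after dosing, protocol Table 2, footnote 6 says: "The Study Completion visit can occur 4 to 12 weeks from the last study dose". Section 6.4 gives the same interval. Section 10.3 collects adverse events up to the final visit. Section 6.3 and Appendix 2 keep patients who stop treatment in follow-up through EOS.

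**The concern.** An incidence rate needs a denominator that covers the period in which its cases are counted. Here the two end on different dates: cases accrue to EOS or Early Termination, and person-time accrues only to the last injection. Every completing subject has 4 to 12 weeks in which a first event can be counted but no time is contributed. The gap can be longer for a subject who stops treatment and stays in follow-up.

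Protocol section 6.2 says the open-label phase is there to collect long-term safety data. An exposure-adjusted rate is used to compare groups or studies with unequal follow-up. The error depends on how long a subject was dosed, so it need not cancel in such a comparison.

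**Working it through.** The documents give no numerical rate or person-year total, so there is no planned figure to reproduce. The check is direct arithmetic on the schedule.

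**Inputs**
- Fibrosis patients are dosed on Day 1, at Week 4 and Week 16, then every 12 weeks to Week 196 at most (protocol 6.1, 6.4). That gives 18 doses, with Week 100 as the tenth, as the protocol states.
- Open-label dosing follows the post-dose biopsy at Week 48, 72 or 96. The next scheduled doses are Weeks 52, 76 and 100.
- Last dose to Study Completion: 28 to 84 days.
- Assumed: nominal visit dates, and a start at the first open-label dose.

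**Per subject.** Let F be the week of the first open-label dose and L the week of the last dose.
- Formula days = 7(L − F) + 1
- Days in the TEAE window = formula days + 28 to 84
- Formula rate ÷ matched rate = window days ÷ formula days

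| Open-label dosing | Formula days | Window days | Ratio |
|---|---|---|---|
| Weeks 52-196 | 7×144 + 1 = 1,009 | 1,037-1,093 | 1.03-1.08 |
| Weeks 76-196 | 7×120 + 1 = 841 | 869-925 | 1.03-1.10 |
| Weeks 100-196 | 7×96 + 1 = 673 | 701-757 | 1.04-1.12 |
| Weeks 52-100 | 7×48 + 1 = 337 | 365-421 | 1.08-1.25 |

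**As a rate.** Assume 24 subjects on the same schedule, 3 of them with a given preferred term.
- Weeks 52-196: 3 ÷ (24×1,009/365.25) = 4.5 per 100 person-years, against 4.2-4.4 with matched person-time.
- Weeks 52-100: 3 ÷ (24×337/365.25) = 13.5, against 10.8-12.5.

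**Pooled under the stopping rule.** The protocol synopsis stops dosing for everyone when the last enrolled fibrosis patient reaches Week 100, so earlier enrollees are dosed longer. Assume 24 subjects enrolled evenly over S weeks, F = 52, and no early move to an extension study. L is then the last scheduled dosing week not later than S + 100 minus the enrolment week. The matched totals add 24×28 = 672 to 24×84 = 2,016 days.
- S = 24: 9,180 days against 9,852-11,196, ratio 1.07-1.22.
- S = 48: 11,196 against 11,868-13,212, ratio 1.06-1.18.
- S = 96: 15,228 against 15,900-17,244, ratio 1.04-1.13.

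Later first open-label doses or an early rollover would raise these ratios, so the ranges are illustrations and not bounds.

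**Against a first-event-censored rate.** The numerator counts subjects, so time after a subject's first event is not time at risk for that count. Assume a proportion p has the event, with onset uniform over the window. Censored person-time is then (1 − p/2) of the window time. With p = 3/24 the factor is 22.5/24 = 0.9375.
- Weeks 52-196: 0.9375 × (1.028 to 1.083) = 0.96-1.02.
- Weeks 52-100: 0.9375 × (1.083 to 1.249) = 1.02-1.17.

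The formula breaks even at p = 2(1 − formula days/window days). For Weeks 52-196 this is 2(1 − 1,009/1,037) = 5% to 2(1 − 1,009/1,093) = 15%. For Weeks 52-100 it is 2(1 − 337/365) = 15% to 2(1 − 337/421) = 40%. Above the break-even the formula understates the censored rate.

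**The case against.** The best defence is that first-to-last-dose is a familiar measure of treatment duration, that it is openly defined, and that the output is descriptive in a phase with a single selected dose and no concurrent control. The last part stands and limits the severity. The first part does not rescue the formula. Duration of dosing can be reported as such, but as a denominator it must span the counting window. Protocol section 4.9 bases the dosing interval on activity lasting until rebound begins about 12 weeks after a dose, yet the formula credits the last dose with one day.

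A second defence is that SAPv3.0, which is not among the documents, may resolve the point. The addendum says "For other general definitions and data handling, refer to SAPv3.0", but that covers only what the addendum leaves open. Both the TEAE window and the exposure formula are written out in the addendum itself.

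Three stronger readings are tempting and are not supported.

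- **The rate is always too high.** This holds only against uncensored person-time. Against first-event-censored time the direction can reverse for common preferred terms, as shown above.
- **A subject with one open-label dose contributes 1 day against 29-85 days at risk, so rates could be inflated many times over.** The day count is right, but the rate divides by total exposure across subjects. A completing subject with one dose omits the same 28-84 days as any other completer.
- **Person-time starts at double-blind Day 1, which would push an open-label rate downward** (365-421 window days against 7×100 + 1 = 701 for last dose at Week 100). The formula does say study drug without qualification. However, the addendum's purpose, analysis set and Table 1 all point to the first open-label dose, and SAPv3.0 may settle it. This is a wording gap to close, not a demonstrated error.

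Nor can one say that this is the only exposure-normalised adverse-event output. Section 6.4.1 repeats the SAPv3.0 adverse-event analyses for the open-label phase, and those cannot be seen here.

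**Conclusion.** The mismatch is real and sits entirely within the addendum: nothing in the documents adds a post-dose interval to person-time or cuts the numerator off at the last dose. The 3-8% (Weeks 52-196) and 8-25% (Weeks 52-100) overstatements are relative to uncensored person-time over the TEAE window, and rest on nominal visits, a 28- to 84-day tail and a start at the first open-label dose. Confidence is high on the end-date mismatch and lower on the size, because actual enrolment timing, extension rollover and early stopping are not given.

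Severity is minor. The error affects the level of one descriptive rate and its comparison with rates from other phases or studies. Crude incidences, event counts, severity and relatedness summaries do not use this denominator. Within a column the order of preferred terms is unchanged, since all share it. No test or dose decision depends on the rate.

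**What to change.** Replace the exposure sentence in section 6.4.1 with person-time = (EOS or Early Termination date − date of first open-label fazirsiran dose + 1) / 365.25, so that it matches Table 1. An acceptable alternative is to restrict counted TEAEs to a stated window after the last dose and end person-time at the close of that same window.

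Because the numerator counts subjects, it is preferable to end person-time at first onset of the event for subjects who have it. Person-time then becomes specific to each preferred term. If this is not done, the table should say that person-time is not censored at first event.

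In the same sentence, state that the start is the first open-label dose, or cite the SAPv3.0 definition.

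The cost is one sentence in the SAP addendum and one derivation change. The dates are already collected, and no visit, assessment or treatment rule changes.

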11.1. Study Populations

Four study populations will be defined and evaluated in this study.

- Safety Population: All patients who receive at least one dose of study drug. The Safety Population will be used for safety analyses. Patients will be included in the analyses according to the treatment they actually received.
- Full Analysis Set (FAS): All randomized patients who receive at least one dose of study drug. The FAS will be used to analyze endpoints related to efficacy. Patients will be included in the analyses according to the treatment planned by randomization.
- Modified Full Analysis Set (mFAS): All randomized patients who receive at least one dose of study drug who has pre-dose serum Z-AAT assessment and a Week 16 post-dose assessment.
- **PK population:** All FAS patients who have sufficient plasma concentration data to facilitate determination of PK parameters. Patients with major protocol violations will be assessed on a patient-by- patient basis for inclusion in the PK Analysis set. PK population will be used for PK analyses.

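### The open-label exposure-adjusted TEAE rate counts events from the first open-label dose but, read literally, counts person-time from the first blinded dose, so the rate is generally understated

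*SAP*

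**What the plan says.** The addendum describes the open-label phase. Its analysis set is "All subjects who receive at least one dose of Fazirsiran in the open-label phase" (Section 3.1). Table 1 in Section 4 ties four terms to the first open-label dose: baseline, study day, TEAE and serious TEAE. A TEAE is an "Adverse event that first occurred or worsened in severity following dose administration of" "the first dose of open-label phase Fazirsiran through EOS or Early Termination".

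Section 6.4.1 then says that "Adverse events analyses described in the SAPv3.0 will be repeated for adverse events captured during open-label phase". Among these analyses is an exposure-adjusted incidence rate by preferred term: the number of subjects with the event divided by the total exposure time over subjects. In that rate "each subject's exposure in person-year is calculated as (date of last dose of study drug" minus the "date of first dose of study drug +1) / 365.25". Neither date carries the open-label qualifier used in Table 1.

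The addendum does not define study drug. Section 4 adds: "For other general definitions and data handling, refer to SAPv3.0". SAPv3.0 is not among the documents available for this review.

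**The concern.** Numerator and denominator should cover the same period. Patients in the open-label set are those with fibrosis who began dosing on Day 1 of the double-blind phase and moved to open-label dosing only after the post-dose biopsy (Protocol Synopsis and Section 6.1). If the clock starts at their first dose of study drug, all their blinded time enters the denominator, although an event in that time cannot be an open-label TEAE.

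This is the only exposure-adjusted safety rate in the addendum, and Protocol Section 6.2 gives long-term safety as the purpose of the open-label phase. A denominator that is too large makes events at the open-label dose look rarer than they were, and it spoils any comparison of the rate with a blinded-phase rate or with another study.

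**Working it through.** **Inputs.** Fibrosis patients are dosed on Day 1, at Weeks 4 and 16, then every 12 weeks to Week 196 (Protocol 6.4, Table 2). The post-dose biopsy is at Week 48, or at Week 72 or 96 for patients already past Week 48 when Protocol v4.0 was approved. Study Completion is 4 to 12 weeks after the last dose (Table 2, footnote 6).

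**Reproducing the calendar.** Day 1, Week 4 and Week 16 are 3 doses. Weeks 28 to 196 in steps of 12 add (196 − 28)/12 + 1 = 15, giving 18 in total. The 10th dose falls at 28 + 6 × 12 = Week 100. Duration is 8 + 196 + 12 = 216 weeks. All three agree with the protocol. The next scheduled dose after a Week 48, 72 or 96 biopsy is Week 52, 76 or 100. These open-label start weeks are derived from the calendar; the documents do not state them. They also state no value for the rate or its bias.

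**Formula.** Let s be the week of the first open-label dose, e the week of the last dose, and f the weeks from last dose to EOS.

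- Exposure as written, in days: 7e + 1
- Exposure from the first open-label dose to the last dose: 7(e − s) + 1
- Exposure over the full TEAE window: 7(e − s + f) + 1
- Understatement: 1 − (matching exposure)/(exposure as written)

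For s = 52 and e = 196 this is 1 − 1009/1373 = 26.5%. For s = 100 and e = 112 it is 1 − 85/785 = 89.2%.

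| Start week | Last dose week | Person-years as written | From open-label start to last dose | Understated | With f = 4 | With f = 12 |
|---|---|---|---|---|---|---|
| 52 | 196 | 3.76 | 2.76 | 26.5% | 24.5% | 20.4% |
| 76 | 196 | 3.76 | 2.30 | 38.7% | 36.7% | 32.6% |
| 100 | 196 | 3.76 | 1.84 | 51.0% | 48.9% | 44.9% |
| 52 | 100 | 1.92 | 0.92 | 51.9% | 47.9% | 39.9% |
| 100 | 112 | 2.15 | 0.23 | 89.2% | 85.6% | 78.5% |

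A patient with a single open-label dose has one day of exposure between first and last open-label dose, which gives 99.7% to 99.9% before follow-up is counted.

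**Direction.** Against the full TEAE window, exposure as written is too long whenever 7e + 1 > 7(e − s + f) + 1, that is, whenever f < s. Scheduled follow-up is 4 to 12 weeks and s is at least 52.

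**If study drug means fazirsiran only.** Former placebo patients would then start at the open-label dose. With the 2:1 allocation, the average exposure as written for s = 52, e = 196 is (2 × 1373 + 1009)/3 = 1251.7 days, and the understatement is 1 − 1009/1251.7 = 19.4%. For s = 100, e = 112 it is 84.6%. Counting 12 weeks of follow-up as well, the first case still gives 1 − 1093/1251.7 = 12.7%.

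**Pooled illustration (assumed inputs).** Take 24 patients, the protocol's minimum with fibrosis, with last doses spread evenly from Week 196 down to Week 100. Exposure as written totals 65.6 person-years. From open-label start to last dose the totals are 41.7 (all start Week 52; 36.5% understated), 30.7 (starts split equally over Weeks 52, 76 and 100, the latest starts given to the longest-treated; 53.3%) and 19.6 (all start Week 100; 70.1%).

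**Effect across events.** The same total exposure divides every preferred term's count, with no censoring at first event. Every rate is therefore scaled by one factor.

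**Changing only the start date.** For s = 100, e = 112 this leaves 85 days of exposure against a TEAE window of 113 to 169 days. The rate is then too high by 113/85 − 1 = 33% to 169/85 − 1 = 99%.

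**The case against.** The strongest reply is that the Day 1 start is inferred. Study drug is undefined in the addendum, other definitions are left to SAPv3.0, and the formula may be text carried over from there and meant to apply within the open-label phase. The protocol uses the term both ways: its Safety Population, "All patients who receive at least one dose of study drug", must include placebo patients, while Section 8.4 on accountability names study drug and placebo separately. This stands to the extent that Day 1 is the literal reading and not quoted text. It does not remove the point. If only open-label doses were meant, the formula needs that qualifier. If only fazirsiran was meant, patients randomized to active still start at Day 1.

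A second reply is that a whole-study rate was intended, since Section 6.4.1 also promises overall summaries across both phases. Those summaries list only numbers and percentages of subjects, and the addendum's TEAE starts at the open-label dose, so the numerator would still not match.

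A third reply is that exposure stops at the last dose while TEAEs count through EOS, which works in the opposite direction. This is correct and is a second mismatch. At the scheduled 4 to 12 weeks it offsets only part of the first. For a patient who stops treatment early and is followed for longer than the blinded time, it could outweigh it.

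Finally, the output is descriptive, the addendum plans no comparison with blinded-phase rates, and subject incidence and event counts are reported without this denominator. That limits the consequences.

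**Conclusion.** The point holds. As written, the rate divides open-label events by time that includes the blinded phase, and it is too low in every scheduled case checked. Single-patient cases run from about 26% to 89%, or about 20% to 86% once post-dose follow-up is counted. These rest on the protocol calendar, the literal reading of study drug and, at the upper end, at least two open-label doses.

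Three stronger conclusions might be inferred and are not supported:

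- That the reported rate will be wrong by a quarter to nine-tenths. The reported rate is pooled, and the documents give no distribution of biopsy weeks or last doses. The pooled figures above rest on assumed inputs.
- That the error distorts some adverse events more than others. It is one factor for all preferred terms, so ratios and ranking between events are unaffected. Only the level, and comparisons outside this phase, are affected.
- That correcting the start date alone gives the right rate. It leaves the end of the clock short of the TEAE window.

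**What to change.** In Section 6.4.1, define each subject's open-label person-time as running from the date of the first open-label fazirsiran dose to the end of the TEAE window (EOS or Early Termination), so that numerator and denominator cover the same period. State that the rate uses the Open-label Phase Set, and define study drug wherever the addendum keeps the term. If a whole-study rate is also wanted, report it separately with whole-study events and matching time.

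The cost is one reworded sentence and one changed derivation, using dates that the trial already collects. The reported rates will generally be higher than under the present formula.
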